Previous studies have found that dating application users were significantly more likely to have at least one prior diagnosis of sexually transmitted infection as compared to non-users and also had more sexual partners (3). Homosexual men using dating applications were also more likely to have unprotected sexual intercourse (4). A meta-analysis found that the odds for seroconcordant and serodiscordant unprotected anal intercourse was higher in online initiated encounters as compared to offline initiated encounters among men who have sex with men (MSM) (5). In a study regarding HIV risk among MSM in East and South-East Asia, findings suggested that online partner finding websites alone did not facilitate greater risk taking, but provided more avenues for MSM who engage in risky HIV behavior to find more partners (6). In a study conducted in Hong Kong college students, dating application usage was significantly associated with unprotected sexual intercourse with more lifetime partners, less consistent condom usage, and the likelihood of not using a condom in the last sexual encounter (2).

Apart from sexual risk, the usage of dating applications has also been associated with recreational drug use in college students (7). Furthermore, dating application users were more likely to have experienced sexual abuse in the past year as compared to non-users and are also at a higher risk for lifetime sexual abuse (8). The content presented on dating application profiles are also a source of concern, particularly for adolescents. A study analyzing content on a teen dating site found a variety of risk-related content such as sexual content, alcohol use, drug use, and violence (9). Concerns regarding personal information and monetary scams are also prevalent. This reveals a strong association between using dating applications and detrimental behavior, indicating the need for the development of interventions to encourage the safe usage of dating applications.

As adolescents and young adults spend a significant amount of time online, health interventions on the Internet represent a promising avenue to reach this population. A review of RCTs revealed that interactive computer based interventions were effective tools for sexual health learning and had positive effects on self-efficacy, intention, and sexual behavior (10). Other advantages of internet based interventions is the level of accessibility, confidentially, and availability of tailored messages or content (10). Peer led interventions have also been shown to be an appealing approach in health promotion for adolescents and young adults, as individuals in this age group tend to seek advice and information from their peers instead of from adults or other figures of authority (11). A peer led approach in the form of crowdsourcing has been shown to be useful in reaching and engaging communities in public health interventions (12). Crowdsourcing is conducted by having a large group of people work together to solve a problem (13). Ideas, concepts, designs, and other elements are collected from the group and synthesized into a final product that is presented to the community. Crowdsourcing may have some advantages over traditional methods of public health intervention development. Firstly, this is a bottom up approach that will involve community members instead of experts or academics. This may result in novel and more relatable ideas for the intervention. Secondly, crowdsourcing will also increase community involvement and awareness of a specific issue or public health topic (14). A systematic review found that crowdsourcing improved the quality, cost, and efficiency of research projects while engaging a large part of the public to create innovative material (15). Crowdsourcing has been a popular approach in developing HIV interventions and it has been shown to be feasible in engaging community members and in gathering culturally and locally relevant material (16). Crowdsourcing was also used in the CrowdOutAIDS project launched by UNAIDS to gather content incorporating youth perspectives and to increase community empowerment and mobilization (17).

Due to the aforementioned reasons, we believe that that a web based peer-led intervention to educate the public on dating application risks would be effective and appropriate. In this study, we evaluate the effectiveness of a web-based peer-led intervention to promote safe usage of dating applications among young adults aged 18-27 in Hong Kong. The trial will be conducted in compliance with the protocol, GCP, and the applicable regulatory requirements.

Trial Objectives and Purpose

Aim: To promote safe usage of dating applications among young adults in Hong Kong

Objectives

- To evaluate the effectiveness of a web-based, peer-led intervention in:
 - Providing appropriate and reliable information about dating applications to young adults in Hong Kong
 - Increasing the awareness of dating application associated risks and benefits among young adults in Hong Kong
 - Improving the attitudes towards risk perception and the safe usage of dating applications among young adults in Hong Kong

• Promoting behavioral skills related to the safe usage of dating applications in young adults in Hong Kong, specifically in preventing and handling negative experiences associated with dating applications

Trial Design

Study design

The study will use an open-labeled randomized control trial design with one intervention arm and one control. The control will have access to an online resource with similar interactive elements and time usage on a different topic. Both arms will complete the baseline and final questionnaire. There will not be any blinding as it is an open labeled study but participants will be randomly assigned to the intervention or control arm with a randomization software. Students in the Yijin program may be randomized by clusters to minimize the chance of contamination.

Intervention

The intervention is a web-based resource including text content, 4 videos, a scenario game and a risk assessment. The program can be accessed on both phones and other mobile devices such as smart phones and ipads. The topics of each segment is listed below:

Video 1: Introduction of the theme that meeting people on dating apps and meeting friends in real life present the same risks. The focus is that users should not have assumptions when meeting people in either context. This video also touches upon social expectations and pressures to pay for dates, leading to potential risk of falling victim to monetary scams.

Video 2: This video provides a specific example of the discrepancies in behavior in real life vs. when using dating apps. The situation is that one may be less alert when speaking to a stranger on an application.

Video 3: This video provides another example of the risks associated with using dating applications and how this compares to behavior in real life.

Video 4: This video is about the legal issues and risk of sexual assault. This video will also provide information on the steps to take following a negative experience and the available resources.

Scenario game: Participants will make a personalized profile and choose their app at the start of the game. They will then start conversation to start the game and go through a series of situations where they can pick between 5 choices. With a preset algorithm, the choices that the users make will ultimately get them to a certain outcome.

Topics that are explored in the game include: unsafe sexual behaviors, scams, leakage of personal data, intimate photos, and secret photographs.

Risk assessment: A 14-item risk assessment will generate an overall score for participants to infer of their level of risk in using dating applications.

Control

The control group will be the "Health Exercise for all" campaign website by the Hong Kong Government (18). The website provides information for types of exercises that are suitable for all ages and at different settings such as the workplace. The website provides informational pamphlets in PDF format, instructional videos on how to carry out different exercises, and interactive games (18).

The control website begins with an introduction regarding the background of the campaign and it's aims. Contact information for relevant offices for enquiry are provided. The campaign includes nine virtual classes that include 1) Introduction, 2) Points of Note and Exercise Guide and a set of videos of the exercise demonstrations. Videos range from 20 seconds to 10 minutes. Participants in the control group will be sent links to the virtual classes with instructions on which time matched video to watch. The website provides eight different interactive games such as "Calorie Restaurant", "Do I have a big tummy", and "I want to be more active". The "I want to be more active" game is most similar to the scenario game developed in the dating application intervention with seven questions to determine whether one is suitable to engaging is more active athletic activities.

Delivery of Intervention

There will be two modes of intervention delivery. In the educational settings, a research assistant and a member of the investigative team will attend a class session to provide a quick introduction to the study and deliver the web-based resource. Participants will be asked to bring their computers or phones and will be provided with the link to the intervention during a class session. Participants will be told that participation is voluntary and that their participation will not have any effect on their grades for the class.

For participants recruited from NGOs, the intervention will be delivered electronically. An email containing the same information as presented by the investigative team member in the educational settings will be sent to the participants along with the access link to the intervention.

Consent for participants in educational settings will be obtained with a written consent form. The investigative team will pass out the consent forms to the participants after the brief introduction of the study and before the delivery of the intervention content. Participants will be given time to read over the information and the signed consent form will be collected by the investigative team. There may be a possibility that a few students in the Yijin Program are under 18 as the program accepts students who just graduated from secondary 6. If this occurs and the student would like to participate, the school will provide consent for the student *in loco parentis*, or in the place of the parent or legal guardian.

Participants recruited from NGOs will be sent an electronic consent form. The online consent form is made on the program Survey Gizmo and participants can access this form either from a share link or through a QR code. Information on the study is provided in the online form and participants are prompted to tick the necessary items to indicate their understanding and agreement. Participants will then be able to sign the form electronically with their computer mouse or touch screen. The age range for recruitment for NGOs will be 18-27 therefore there should not be anyone below 18.

The primary endpoint will be 1 month after the delivery of the intervention. Students will fill out a baseline questionnaire before the delivery of the intervention and an immediate post questionnaire. 1 month later, students will access a follow-up questionnaire via HKU Survey Gizmo, a secure survey tool to ensure all data is kept confidential. The details of the delivery method of the follow-questionnaire will be discussed with the college's staff. Research staff may attend a special session or class to delivery the follow-up questionnaire. Another option is to have teachers deliver the follow up questionnaire. The follow-up questionnaire will be online hence participants will be able to access it on their computers, phones, or other mobile devices. Participants are estimated to participant in the trial for no longer than 4 months. Participants are allowed to withdraw from the study at any point in time without any criterion.

Selection and Withdrawal of Subjects

Inclusion criteria

- Aged 17-27
- Able to read and understand Chinese
- Able to provide an active email

Exclusion criteria

- People who have a physical impediment in which they cannot access the material in the intervention

Participants are allowed to withdraw from the study at any point in time without any criterion. We will utilize the "intention to treat" approach to deal with subjects withdrawn.

Treatment of Subjects

The intervention is a web based intervention and will not involve any medical treatments, drugs, or pharmaceuticals. The route of administration is access through any device that can access web-based content and the dosage is one visit.

Assessment of Efficacy

Evaluation will be done with an online survey tool called HKU Survey Gizmo. There will be a pre questionnaire containing baseline demographics and other questions concerning dating application usage. The participants will be given 30-45 minutes to access the program. Following that, the participants will be given a post questionnaire. 1 month later, the participants will be asked to fill in a follow up questionnaire.

Assessment of Safety

Participants will be given contact information to a dedicated staff if they have any questions of concerns regarding the study and their participation in the study. Additional psychological risk may occur as the study involves bringing up sensitive topics such as risky sexual behavior and personal data, to minimize this risk, participants will be ensured that their information is protected with the utmost care and that all their gathered information will only be used for researched purposes. Any adverse events will be recorded.

Statistics

Sample size calculation

The sample size was be calculated with the following components:

- α (two-tailed) of 0.05
- $\bullet \qquad \beta = 0.8$
- Obtained from a study with a peer-led safe sex online intervention for Hong Kong adolescents aged <25 (19)
 - o Standard deviation: 0.52
 - o Effect size: 0.21

Attrition rate: 15% in online studies (20, 21)

112 people per intervention arm

Data Analysis

Data will be analyzed using SPSS. Descriptive statistics will be carried out analyze the demographics of the target population. Differences in baseline demographic characteristics between the intervention and control group will be assessed using chi-squared tests.

For outcome evaluation, paired t-tests will be used to examine within group outcome changes. For the primary outcome that is a score, linear regression will be used to evaluate the difference between the control and intervention group.

Independent t-tests will be carried out to evaluate the score change within group and also between groups. The outcome difference at baseline and at follow-up will also be evaluated with linear regression.

Direct Access to Source Data/Documents

The investigator/institution will permit trial-related monitoring, audits, IRB/IEC review, regulatory inspections, providing direct access to source data/documents.

Quality Control and Quality Assurance

Ethics

Major ethical issues involve asking about sensitive information regarding risky sex behaviors, users' privacy, and legal issues. Participants will be ensured by the project's researchers that their information is kept strictly confidential. Researchers will also ensure that participants understand the purpose and procedure of every step of the project and participants will be provided with a contact for whenever they have any questions or concerns. Patients also understand that they are allowed to withdraw at any given point of the study.

Data Handling and Record Keeping

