Evaluation of a	ı peer-led we	b-based int	tervention f	or safe usa	ige of d	ating
applica	tions in Hong	g Kong: a r	andomized	controlled	trial	

Statistical Analysis Plan

August 2018

(Version 1. Dated 17.08.2018)

Principle Investigator: [name]
Address: Department of Family Medicine and Primary Care, [name]
Co-Investigators: [name], [name]

Statistical Methods

The demographics were described and differences in baseline were assessed using chi-square tests for categorical variables for e.g. age, gender and sexual orientation; and, *t*-test for scaled outcomes. The satisfaction of the intervention at post-intervention was analysed using chi-square test. ITT with the "last observation carried forward" values was adopted. Due to the skewness distribution of the outcomes, the differences of intervention at follow-ups were assessed using Mann-Whitney U-test. Univariate linear regression and multiple linear model was used to evaluate the significant factors between the intervention and control groups and after the adjustment of baseline outcome measurements respectively. All data were entered, cleaned and analysed using SPSS (Version 25) and significant tests were set at P-values <0.05.

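### The protocol leaves open cluster randomisation of Yijin students, but neither the sample size nor any planned between-arm test allows for clustering

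*Protocol*

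**What the plan says.** Under Trial Design, Study design, the protocol states that "participants will be randomly assigned to the intervention or control arm with a randomization software", which reads as individual randomisation. It then adds that "Students in the Yijin program may be randomized by clusters to minimize the chance of contamination". It does not say when that option applies, what the cluster would be, or how many clusters there would be.

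Delivery of Intervention describes two routes. In educational settings participants "will be provided with the link to the intervention during a class session", so a class is a plausible cluster, although the protocol does not say so. The other route is individual: "For participants recruited from NGOs, the intervention will be delivered electronically". The cluster option does not extend to those recruits.

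The Sample size calculation lists alpha, beta, a standard deviation, an effect size and attrition, and arrives at "112 people per intervention arm". It has no ICC, cluster size or design effect.

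For comparisons between arms, Data Analysis says "linear regression will be used to evaluate the difference between the control and intervention group" and "Independent t-tests will be carried out to evaluate the score change within group and also between groups". The SAP's Statistical Methods section uses a Mann-Whitney test, a univariate regression and a linear model adjusted for the baseline outcome. It also says "ITT with the 'last observation carried forward' values was adopted". Neither document mentions a mixed model, generalised estimating equations, cluster-robust variance or a cluster-level analysis.

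**The concern.** The analysis has to respect the unit that was randomised. When whole classes are allocated, students in a class share an allocation and probably share teachers, peers and the session itself. Part of any difference between arms is then a difference between classes. A test that counts each student as independent understates the standard error, so its false-positive rate exceeds the nominal 5%. The effective sample is also smaller than the headcount, so power is lower than the sample size calculation implies.

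The protocol keeps this design available, while both documents specify only analyses that are valid without it. Adjusting for the baseline score may reduce the within-cluster correlation, but it does not deal with what remains.

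**Working it through.** **Reproducing 112.** The inputs from Sample size calculation are two-sided alpha 0.05, SD 0.52, effect 0.21 and attrition 15%. The stated beta of 0.8 is read as 80% power, because taken literally it gives 16 per arm. The effect of 0.21 is read as a raw difference (0.21/0.52 = 0.404 SD), because as a standardised effect it needs 356 per arm before attrition.

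- n = 2(1.96 + 0.8416)² / (0.21/0.52)² = 96.25, so 97 per arm.
- 97 × 1.15 = 111.55, so 112.

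The stated figure is matched with a design effect of 1.

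**Power without clustering.** Power = Φ(0.21/(0.52√(2/n)) − 1.96). This gives 86% at n = 112 (all analysed, as under the SAP's carried-forward values, assuming those values show the full effect). It gives 79% at n = 95 (112 × 0.85 = 95.2 completers).

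**Effect of clustering.** The following are assumptions, not in the documents: cluster size m from 10 to 30, ICC from 0.01 to 0.05, and a clustered share f of a quarter, half or all.

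- Unadjusted test: DE_u = 1 + f(m−1)ICC, and actual alpha = 2(1 − Φ(1.96/√DE_u)).
- Mixed model with ICC treated as known: DE_m = 1/[(1−f) + f/(1+(m−1)ICC)], and SE = 0.52√(2·DE_m/n).

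At m = 10, ICC 0.01, DE_m is 1.02, 1.04 and 1.09 for quarter, half and all. At m = 30, ICC 0.05, DE_u is 1.36, 1.725 and 2.45, and DE_m is 1.17, 1.42 and 2.45. Each range below runs from the mildest to the most severe combination.

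| Clustered share | Alpha, unadjusted test | Valid power, 112 per arm | Valid power, 95 per arm |
|---|---|---|---|
| None | 5% | 86% | 79% |
| Quarter | 5.3%–9.3% | 85%–80% | 79%–73% |
| Half | 5.5%–13.6% | 84%–72% | 78%–65% |
| All (upper bound) | 6.0%–21% | 82%–49% | 76%–43% |

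The severe end of the quarter row is nominal: a quarter of 112 is 28 per arm, so a cluster of 30 does not fit.

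**The planned Mann-Whitney test.** Simulated at 112 per arm with clusters of 14 or 28 and ICC 0.01 to 0.05, alpha is 5.6%–6.8% for a quarter clustered (clusters of 14 only), 5.8%–13.0% for half and 6.5%–19.7% for all. The rank test is affected in the same way as the t-test.

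**Few clusters.** The large-sample figures ignore the loss of degrees of freedom. With everyone clustered and 112 per arm, a noncentral t with 2k − 2 degrees of freedom (k clusters per arm) gives:

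| Layout per arm | df | ICC 0.01 | ICC 0.02 | ICC 0.05 |
|---|---|---|---|---|
| 8 clusters of 14 | 14 | 75% | 71% | 59% |
| 4 clusters of 28 | 6 | 61% | 53% | 38% |

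**Whether a valid analysis is available.** In the Mann-Whitney scenarios, a mixed model with arm, recruitment source, a random cluster intercept and Satterthwaite degrees of freedom (baseline omitted) had simulated alpha of 2.0%–5.2%. Its power was 81%–82% with a quarter clustered and 69%–79% with half clustered.

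**The case against.** The strongest reply is that the consequence is doubly conditional. The operative rule is assignment of participants, clustering is only permitted, and the SAP mentions no clusters. If the option is never used, nothing is wrong on this point; if it is used with a small ICC and small clusters, the error is slight. That is correct, and it limits any statement about size. It does not remove the gap, because the choice of randomisation unit is left open and one of the two choices has no valid analysis in either document.

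Several narrower objections stand:

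- The all-clustered case would require no NGO recruits, so its figures are only an upper bound.
- With 112 analysed, a design effect of up to 112/96.25 = 1.16 still leaves 80% power. For a quarter clustered the 80% target is therefore essentially met; alpha still exceeds 5%.
- Attrition would also shrink the clusters, which makes the severe end of the 95-per-arm column somewhat pessimistic. With clusters of 25.5 instead of 30, the 43% becomes 46%.
- The protocol speaks of educational settings in general. If classes outside the Yijin programme recruit, a two-level source covariate will not be enough.
- The SAP is written in the past tense. If allocation has begun, the correction has to be made before analysis, and it depends on cluster membership having been recorded.

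**Conclusion.** The concern holds, and resolving it is necessary. The documents themselves establish the open option, a sample size with a design effect of 1, and between-arm tests that all assume independence. The direction of the error is certain if clusters are randomised and the ICC is positive: alpha above 5% and power below the individually randomised value.

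The size cannot be fixed from the documents and runs from negligible to large, depending on assumed cluster size, ICC and clustered share. Baseline adjustment may raise power and lower the residual ICC, so the milder figures may apply to the SAP's adjusted model. The conclusion rests on the closed-form results and does not depend on the mixed-model or permutation simulations, which only illustrate the remedy.

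**What to change.** State in the protocol, before the start (or before analysis if allocation has begun), whether Yijin students are cluster randomised.

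**If they are:**

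1. Define the cluster, for example the class, and record a cluster identifier.
2. Replace the unadjusted between-arm tests with one cluster-valid analysis. One example is a linear mixed model with arm, baseline score and recruitment source as fixed effects, a random cluster intercept, NGO participants as clusters of one, and small-sample degrees of freedom. Cluster-robust variance with a small-sample correction, or a cluster-level analysis, is an alternative. The choice is open, provided it is named in advance. If the SAP's chi-square test of satisfaction compares arms, it needs the same treatment.
3. Restate the power for 112 per arm under a stated ICC, cluster size, number of clusters and clustered share.
4. Optionally, since the SAP cites skewed outcomes, add a rank permutation test that re-randomises whole clusters for Yijin and individuals for NGO recruits. It is weak with few clusters: simulated power with everyone clustered is 23%–43% with 4 clusters of 28 per arm and 57%–72% with 8 of 14.

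**If they are not:** say that randomisation is individual throughout, and acknowledge that the only safeguard against contamination in the documents is not used. The planned tests then need no change on this point.

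The cost is protocol and SAP wording, one variable, a mixed model in SPSS and, if wanted, a short permutation script. Intervals widen and the stated power becomes less favourable. Correcting the false-positive rate needs no extra enrolment, but it does not restore power lost to clustering. Giving up the option leaves students in the same class exposed to contamination.

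### Recruitment setting (class or NGO) is neither a stated stratification factor nor a named covariate: a modest loss of precision if individuals are randomised, and a possible type I error problem if Yijin clusters are

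*Protocol*

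**What the plan says.** Protocol, Delivery of Intervention: "There will be two modes of intervention delivery". In educational settings, study staff introduce the trial in a class session and hand out the link there. NGO recruits receive the same introductory information and the link by email, and no staff presence is described. Consent is on paper in class and electronic for NGO recruits. The same section says the 1-month questionnaire for students may be given in a session run by research staff or by teachers; nothing comparable is described for NGO recruits.

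Protocol, Trial Design (Study design), on allocation: "participants will be randomly assigned to the intervention or control arm with a randomization software". Stratification, blocking and minimisation are not mentioned. The one rule specific to a setting is optional and is given for another purpose: "Students in the Yijin program may be randomized by clusters to minimize the chance of contamination".

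Protocol, Data Analysis, plans a linear regression of the primary score on arm and names no setting term. SAP, Statistical Methods, compares the arms at follow-up with a Mann-Whitney U-test and fits a multiple linear model "after the adjustment of baseline outcome measurements respectively". Neither document mentions a setting covariate, a stratified test or an analysis by setting.

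**The concern.** Setting is known for everyone before allocation. It determines how the material is delivered and whether anyone is present, so it could plausibly be related to the 1-month score and to dropout. A variable of that kind is normally balanced in the allocation and carried into the model.

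What is at stake depends on the unit of randomisation, which the protocol leaves open. With individual allocation, between-setting variation stays in the error term and the trial is slightly less efficient than it could be. With whole classes allocated and nothing to balance them, students move between arms in blocks. The proportion of students can then differ widely between arms, and a standard error that treats participants as independently allocated does not reflect that extra variation.

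**Working it through.** **1. The plan's own figure.** Inputs from the protocol's sample size section: "α (two-tailed) of 0.05"; 0.8, printed as β and read here as power; "Standard deviation: 0.52"; "Effect size: 0.21", read as a raw mean difference; "Attrition rate: 15% in online studies".

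- n per arm = 2 × [0.52 × (1.960 + 0.842) / 0.21]² = 96.25, rounded up to 97.
- 97 × 1.15 = 112, as stated.
- Completers per arm: 112 × 0.85 = 95.2. Power at that number, with no covariates, is 79.6%.
- Planned effect in SD units: 0.21 / 0.52 = 0.404.

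**2. Individual randomisation.** The documents give neither the share of participants from each setting (p) nor the outcome gap between settings (g, in SDs). I take p = 0.5, which makes the loss largest, and a range for g.

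- Chance difference between arms in setting share: SD = √(2p(1−p)/n) = √(0.5/95.2) = 0.072, so the 95% range is ±14.2 percentage points. With 10% in the smaller setting it is ±8.5 points.
- Variance explained by setting: R² = p(1−p)g². Power with setting in the model uses SD = 0.52 × √(1−R²).

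| g (SD) | R² | Power without setting | Power with setting | Loss (points) |
|---|---|---|---|---|
| 0.25 | 0.016 | 79.6% | 80.2% | 0.6 |
| 0.5 | 0.0625 | 79.6% | 82.1% | 2.5 |
| 0.8 | 0.16 | 79.6% | 86.0% | 6.4 |

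A simulation (190 completers, 8,000 runs per scenario) gave a mean error of the unadjusted estimate of 0.002 or less on the score scale, and type I error of 4.8% to 5.2%. The ordinary standard error already allows for chance imbalance here.

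**3. Clusters in the Yijin stratum.** Assumed layout, not in the documents: 6 classes of 20, each allocated by an independent coin toss, and 104 NGO recruits split evenly (6 × 20 + 104 = 224 = 2 × 112).

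- Probability of a 4:2 or more uneven split of classes: 1 − C(6,3)/2⁶ = 1 − 20/64 = 69%.
- SD of the difference between arms in number of students: 20 × √6 = 49 for classes, against √120 = 11 if the same 120 students were allocated one by one.
- A 4:2 split gives 80/132 = 61% students in one arm and 40/92 = 43% in the other, a difference of 0.171.

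Type I error was simulated under no arm effect, with no within-class correlation so as to isolate setting (10,000 runs per row, nominal 5%). The gap is in within-setting SDs and should be read as what remains after baseline adjustment.

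| Residual gap (SD) | Setting omitted | Setting in model |
|---|---|---|
| 0.25 | 7.1% | 5.0% |
| 0.3 | 7.7% | 4.9% |
| 0.5 | 11.8% | 5.2% |
| 0.8 | 20.2% | 5.0% |

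At 0.5 SD, the SD of the estimated arm difference was 0.18 with setting omitted and 0.14 with it included. The mean error stayed below 0.004 SD in every row. Over repeated randomisations the estimate is therefore unbiased, and the fault lies in the standard error.

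**4. How far baseline adjustment shrinks the gap.** Assume a gap g = 0.5 SD at both baseline and follow-up, an even split, and within-setting correlation r between the two scores. The pooled slope is b = (r + g²/4)/(1 + g²/4), and the residual gap is g(1 − b). For r = 0.3, 0.5 and 0.7, b = 0.34, 0.53 and 0.72, and the residual gap is 0.33, 0.24 and 0.14 SD.

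**The case against.** A reader might infer that chance imbalance by setting biases the treatment comparison. The documents do not support that. Randomised allocation is unbiased over repetitions with either unit, and with individual allocation the test also holds its level. Only a shift in one particular imbalanced sample can be claimed.

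A reader might also take the 4:2 example further: 0.171 × 0.5 SD = 0.086 SD, which is 21% of the planned 0.404 SD. The arithmetic is right, but it stacks an assumed number of classes, an assumed NGO share, unblocked allocation and a 0.5 SD gap that baseline adjustment does nothing to reduce. With the residual gaps in step 4, the same split shifts the estimate by about 14%, 10% or 6% of the planned effect. The example also gives arms of 132 and 92, against the planned 112 each.

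Further points against:

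- The protocol does not say that the clusters are classes, and it does not exclude blocking. Cluster allocation is an option, not a commitment. This stands, and makes the second half of the point conditional.
- The age contrast is marginal: 17–27 overall against 18–27 for NGO recruits, with at most a few students under 18. It carries no weight here.
- Both settings receive the same introductory information, and the documents contain no evidence that setting predicts the score. This stands; the case rests on plausibility.
- The SAP speaks of evaluating significant factors without listing them, so a setting term is unspecified rather than ruled out.
- If classes are randomised, within-class correlation may matter more. With assumed classes of 20 to 30 and intraclass correlations of 0.01 to 0.05, power would fall to about 72% to 43% if every participant were in a cluster. This stands as a separate matter, and correcting it would not balance setting between arms.

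On the other side, baseline adjustment cannot remove differences that arise after baseline, such as attended versus unattended use of the site, and the Mann-Whitney test adjusts for nothing.

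**Conclusion.** The point holds in a limited form. Stratification by setting is not stated, and setting is not a named covariate, although delivery and supervision differ between settings.

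Under individual randomisation the consequence is lost efficiency only. It is small for gaps up to 0.5 SD, larger at 0.8 SD, and smaller again once baseline is in the model.

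Under cluster randomisation of Yijin students without balancing, the ordinary standard error is too small, and type I error could rise from slightly above nominal to several times nominal. One setting term restores it in the assumed layout. How large the effect would be in this trial cannot be determined from the documents, because the number and size of clusters, the NGO share and the setting gap are not given.

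The case for acting is that the remedy is nearly free, not that harm has been shown.

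**What to change.** - **Allocation.** Stratify the randomisation by setting (educational/Yijin against NGO). If clusters are used, allocate them in blocks within the Yijin stratum. The SAP is written in the past tense; if allocation is already complete, make only the analysis change.
- **Analysis.** Prespecify the linear model with arm, baseline score and setting as the main between-arm comparison, in place of the unadjusted Mann-Whitney test. If a rank test is kept because of skewness, use one stratified by setting.
- **Reporting.** State the unit of randomisation in each setting, and tabulate numbers by arm and setting.

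The cost is one stratification factor in the software and one degree of freedom in the model. Nothing changes for participants. If classes are randomised, within-class correlation needs its own provision in the sample size and standard errors; this change does not supply it.
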